5.4 Missing or Incomplete Date for Last Dose of Study Drug

In the Safety Analysis Set, if the last dose date of study drug is missing for a subject who completed or early terminated from the study, then the date of the end-of-study/early termination visit will be used in the calculation of treatment duration. For the incomplete last dose date of the study drug, the imputation algorithms will be detailed in the analysis dataset specification document. The missing or incomplete dates will be displayed in the data listings as reported on the eCRF rather than the imputed dates.

For the interim safety data review, if a subject is still ongoing, then this subject's last dose date will be imputed using the database extract date.

5.5 Missing or Incomplete Dates for Prior or Concomitant Medications

Missing or incomplete medication start or end dates will be imputed for the purpose of determining whether the medications are taken concomitantly (see [Section 11](#) for definition). When the chronological order of a medication's utilization relative to the study drug treatment period is unclear due to missing or incomplete date(s), the medication will be considered as concomitant. The imputation algorithms will be detailed in the analysis dataset specification document. The missing or incomplete dates will be displayed in the data listings as reported on the eCRF rather than the imputed dates.

5.6 Missing or Incomplete Dates for Adverse Events

Missing or incomplete adverse event (AE) start dates will be imputed for the purpose of determining whether the AEs are treatment emergent (see [Section 14.1](#) for definition). When the chronological order of an AE onset relative to the study drug treatment period is unclear due to missing or incomplete date(s), the AE will be considered as treatment-emergent. The imputation algorithms will be detailed in the analysis dataset specification document. The missing or incomplete dates will be displayed in the data listings as reported on the eCRF rather than the imputed dates.

5.7 Missing Severity Assessment for Adverse Events

If severity is missing for an AE starting prior to the date of the first dose of study drug, then a severity of "Mild" will be assigned. If the severity is missing for an AE starting on or after the date of the first dose of study drug, then a severity of "Severe" will be assigned. The imputed values for severity assessment will be used for incidence summaries, while the actual values will be presented in data listings.

5.8 Missing Relationship to Study Drug for Adverse Events

If the relationship to study drug is missing for an AE starting prior to the date of the first dose of study drug, then a causality of “Not Related” will be assigned. If the relationship to study drug is missing for an AE starting on or after the date of the first dose of study drug, then a causality of “Related” will be assigned. The imputed values for relationship to study drug will be used for incidence summaries, while the actual values will be presented in data listings.

5.9 Character Values of Clinical Laboratory Variables

If the reported value of a clinical laboratory variable cannot be used in a summary due to, for example, a character string reported for a numerical variable, an appropriately determined coded value will be used in the summary. The coding algorithms will be detailed in the analysis dataset specification document. The actual values as reported in the database will be presented in data listings.

6 SUBJECT DISPOSITION

For subjects who participate in the screening phase but are not randomized (screen failures), their demographics information, screen failure reasons (the specific inclusion/exclusion criterion (or criteria) not met) and protocol version will be listed. If a subject is re-screened, then the re-screening subject ID and the final enrollment status (whether eventually enrolled) will also be displayed in this listing. In addition, the frequency that the screen failure reasons are reported will also be summarized. Note that one subject may be deemed ineligible for multiple inclusion/exclusion criteria and may be allowed to rescreen with the permission of the Medical Monitor.

The number of sites that screened at least 1 subject, number of sites that randomized at least 1 subject, number of subjects screened, and number of unique subjects screened will be summarized by region and overall.

For randomized subjects, number and percentage of subjects in Safety Analysis Set, Full Analysis Set, and Per-protocol Analysis Set will be summarized by treatment group and overall. A listing will be provided displaying all subjects excluded from the Safety, Full or Per-protocol Analysis Sets, and will include reason(s) for exclusion. The number and percentage of subjects who are excluded from the Per-protocol Analysis Set will be presented in a summary table by reason, and by treatment group and overall.

Within each analysis set, the number and percentage of subjects who completed the study or discontinued (all discontinued and by discontinuation reason) will also be summarized by treatment group and overall. Summaries by region will also be presented.

7 PROTOCOL DEVIATIONS

Protocol deviations will be reviewed periodically over the course of the study. The review process, definition of the deviation categories, and the classification of a deviation as major (significant) or minor (not significant) are detailed in the Study Deviation Rules Document.

A summary of the number and percentage of subjects with major protocol deviations for each deviation category will be presented by treatment group and overall. A listing of protocol deviations by site and subject will be provided.

8 DEMOGRAPHICS AND OTHER BASELINE CHARACTERISTICS

Demographics and Baseline characteristics will be summarized by treatment group and overall for Randomized Analysis Set, Safety Analysis Set, Full Analysis Set, and Per-protocol Analysis Set using descriptive statistics. For the Full Analysis Set, summaries by region will be presented. Variables include age, sex, race, ethnicity, height, weight, body mass index (BMI), region, Baseline living situation category, Baseline caregiver category, Baseline NPI-C combined agitation and aggression domain score, Baseline MMSE total score, Baseline CMAI total score, Baseline ZBI total score, and concomitant selective serotonin reuptake inhibitor (SSRI) usage (yes/no).

The reported age reflects a subject's age at the informed consent date. Age, Baseline CMAI total score, Baseline MMSE total score, and Baseline NPI-C combined agitation and aggression domain score will be presented as both continuous and categorical variables. Age will be presented as ≤ 85 and >85 years old. Category of Baseline CMAI will be presented as <65 and ≥ 65 . Category of Baseline NPI-C combined agitation and aggression will be presented as <22 and ≥ 22 . Category of Baseline MMSE will be presented as ≤ 10 , 11-20 and >20 .

Alzheimer's disease history will be summarized by treatment group for Randomized Analysis Set, Safety Analysis Set, Full Analysis Set and Per-protocol Analysis Set using descriptive statistics. Variables include:

- Time (year) since diagnosis of probable Alzheimer's disease
- Duration (year) of symptoms of Alzheimer's disease
- Duration (year) of symptoms of agitation/aggression

Informed consent date will be used as the reference date for calculating the durations listed above.

A listing of living situation and caregiver information by subject and visit will also be provided.

9 MEDICAL HISTORY

Medical and surgical history data will be coded using Medical Dictionary for Regulatory activities (MedDRA) version 19.0 or newer. The subject incidence of relevant medical and surgical history data will be summarized by system organ class (SOC) and preferred term by treatment group and overall for Safety Analysis Set, Full Analysis Set, and Per-protocol Analysis Set. A subject will be counted only once per SOC or preferred term for the summary.

A listing of the SOC, preferred term, body system, verbatim term for the medical history condition/event, start and stop dates (when available), and an indicator for whether or not the condition is ongoing will be provided.

10 EXTENT OF EXPOSURE AND TREATMENT COMPLIANCE

Summaries of exposure and compliance to study drug will be provided for the Safety Analysis Set and Full Analysis Set.

10.1 Exposure to Study drug

For each subject, duration of exposure to study drug will be calculated as (last dose date – first dose date + 1). Duration of exposure will be summarized as both continuous and categorical variables by treatment group and overall. For categorical presentation, the number and percentage of subjects in each of the following categories will be presented: <4 weeks (1 to 27 days), 4 to <8 weeks (28 days to 55 days), 8 to <12 weeks (56 days to 83 days), and ≥12 weeks (84 days or longer). Kaplan-Meier curves of duration on study drug will also be presented for each treatment group.

10.2 Measurement of Treatment Compliance

Study drug dosing compliance (in percentage) for a subject is defined as the total number of tablets actually taken divided by the number of tablets expected to be taken and then multiplied by 100. The total number of tablets actually taken is calculated by the total number of tablets dispensed minus the total number of tablets returned. The number of tablets expected to be taken is calculated as the duration of exposure (last dose date – first dose date + 1) multiplied by 2 (the planned number of tablets taken per day).

Compliance will be summarized as both continuous and categorical variables by treatment group. For categorical presentation, the number and percentage of subjects in each of the following category will be presented: <80%, 80 to 120%, and >120%.

11 PRIOR, CONCOMITANT AND POST MEDICATION

For a subject, prior medication is defined as any medication with the start and stop dates prior to the date of the first dose of study drug. Concomitant medication is defined as any medication with a start date prior to the date of the first dose of study drug and continuing after the first dose of study drug or with a start date between the dates of the first and last doses of study drug, inclusive. Any medication with a start date after the date of the last dose of study drug will be considered as post-treatment medication. Prior, concomitant, or post-treatment medications will be summarized separately.

Medications will be coded using WHO Drug Dictionary (WHODD) 2016 March or newer version. The number and percentage of subjects taking each drug class (ATC Level 3) and medication preferred term will be tabulated by treatment group and overall for the Safety Analysis Set. Multiple medication usage by a subject in the same ATC category will be counted only once.

12 EFFICACY ANALYSES

All efficacy summaries will be performed using the planned treatment assignments based on the randomization schedule. No hypothesis testing is planned. Descriptive summaries of all efficacy endpoints will be provided. The summaries based on mixed model for repeated measures (MMRM) or analysis of covariance (ANCOVA) will include point estimates and confidence intervals.

12.1 Efficacy Variables

12.1.1 Primary Efficacy Variable

The primary efficacy endpoint is change from Baseline to Week 12 in the CMAI total score.

12.1.2 Secondary Efficacy Variable

The secondary efficacy endpoint is change from Baseline to Week 12 in the ZBI total score.

12.1.3 Exploratory Efficacy Variables

The exploratory efficacy endpoints include the following:

- mADCS-CGIC agitation score
- Change from Baseline in NPI-C combined agitation and aggression domain scores
- Change from Baseline in NPI-C individual agitation and aggression domain scores
- Change from Baseline to Week 12 in the ADCS-ADL score
- Change from Baseline to Week 12 in NPI-C total score

- Change from Baseline to Week 12 in NPI-C sleep disorders domain score
- Change from Baseline to Week 12 in NPI-C combined delusions and hallucinations domain scores
- Change from Baseline to Week 12 in NPI-C combined dysphoria and apathy/indifference domain scores
- Change from Baseline to Week 12 in individual NPI-C domain scores (other than agitation, aggression and sleep disorders)
- Change from Baseline in CMAI subscale scores
- Change from Baseline in KSS score
- Change from Baseline in the MMSE score
- The proportion of subjects taking any rescue medication

12.2 Adjustment for Covariates

For continuous variables summarized using MMRM or ANCOVA, the Baseline value of the endpoint being summarized (except mADCS-CGIC) and geographic region (North America, Europe, or Rest of World) will be included as covariates as described in [Section 13](#).

12.3 Handling of Missing Data

The primary efficacy variable will be summarized assuming missing at random using an MMRM method. Total scores that are missing, after any imputation of individual missing items as described in [Section 5.2.1](#), will not be imputed.

12.4 Multiple Comparisons / Multiplicity

No hypothesis testing is planned.

12.5 Examination of Subgroups

Subgroup analyses will be performed with respect to the primary and secondary efficacy variables. The subgroups will include the following:

- Geographic region: North America, Europe, or Rest of World
- Race: White or Non-white
- Sex: Female or Male
- Age group: ≤ 85 years or > 85 years
- Baseline Living situation: Home or Assisted living/other
- Baseline Caregiver category: Professional caregiver or non- professional caregiver

- Baseline NPI-C combined agitation and aggression score: <22 or ≥ 22
- Baseline CMAI total scores: < 65 or ≥ 65
- Baseline MMSE scores: ≤ 10 or 11-20 or > 20
- Concomitant selective serotonin reuptake inhibitor (SSRI) usage: Yes or No

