1 INTRODUCTION

This statistical analysis plan (SAP) provides a technical and detailed elaboration of the summaries of efficacy and safety data. Specifications for tables, figures, and listings are contained in a separate document.

Enrollment in the study was terminated early by the sponsor for business reasons not related to the safety of pimavanserin after 111 subjects were randomized. The last subject was randomized into the study on November 2, 2017. As a result, the study is not powered to definitively evaluate efficacy measures and the summaries will be descriptive in nature. No hypothesis testing is planned.

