4 ANALYSIS SETS

Randomized Analysis Set

The Randomized Analysis Set will consist of all subjects who were randomized.

Subjects will be classified according to the randomized treatment assignment.

Safety Analysis Set

The Safety Analysis Set will consist of a subset of subjects in the Randomized Analysis Set who received at least one dose of study drug.

Subjects will be classified according to the actual treatment received.

Full Analysis Set

The Full Analysis Set will consist of a subset of subjects in the Safety Analysis Set who have both a Baseline value and at least 1 post-Baseline value for the CMAI total score.

Subjects will be classified according to the randomized treatment assignment.

Per-protocol Analysis Set

The Per-protocol Analysis Set will consist of a subset of subjects in the Full Analysis Set who do not have any protocol deviation which is considered to have substantial impact on the primary efficacy outcome, change from Baseline to Week 12 in the CMAI total score. The precise reasons for excluding subjects from the Per-protocol Analysis Set will be fully defined and documented *a priori* before the clinical database lock.

Subjects will be classified according to the randomized treatment assignment.

Pharmacokinetics Analysis Set

The Pharmacokinetics Analysis Set will consist of subjects with at least one measurable pimavanserin plasma concentration.

Subjects will be classified according to the actual treatment received.

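### The SSRI subgroup in SAP 12.5 rests on concomitant use, which under SAP 11 includes SSRIs first started on treatment: a minor point with a cheap fix

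*SAP*

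**What the plan says.** SAP 12.5 (Examination of Subgroups) applies ten factors to the primary and secondary variables, CMAI and ZBI total score. Region, race, sex and age cannot change with treatment. Living situation, caregiver category, NPI-C, CMAI and MMSE are each labelled Baseline. The tenth factor is "Concomitant selective serotonin reuptake inhibitor (SSRI) usage: Yes or No", which carries no such label.

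SAP 8, on baseline characteristics, ends its variable list with the same item: "and concomitant selective serotonin reuptake inhibitor (SSRI) usage (yes/no".

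SAP 11 defines concomitant medication by two routes. One is "any medication with a start date prior to the date of the first dose of study drug and continuing after the first dose". The other is a medication "with a start date between the dates of the first and last doses of study drug, inclusive".

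SAP 5.5 adds that when the timing of a medication relative to treatment "is unclear due to missing or incomplete date(s), the medication will be considered as concomitant".

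**The concern.** Concomitant is a defined term in this SAP, and its second route covers drugs begun after randomization. Read as written, a subject who starts an SSRI on treatment is coded *Yes*, both in the subgroup and in a table presented as baseline.

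A new SSRI may be prescribed because agitation is not improving or because of an adverse event, and either can depend on the assigned arm. Protocol Section 1 itself describes one SSRI, citalopram, as effective for agitation and aggression in AD. If membership depends in part on response, the drug–placebo comparison within *Yes* and within *No* is no longer fully randomized. SAP 12 attaches point estimates and confidence intervals to the model-based summaries, so readers will see those comparisons even though nothing is tested.

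**Working it through.** **Can an SSRI starter enter the analysis?**

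- Protocol 3.1 (Screening Period) bars psychotropics during treatment unless the protocol specifies them.
- Protocol 5.7.1 and Appendix C item 4 allow antidepressants on a dose unchanged for at least 4 weeks before Baseline and expected to stay unchanged. Appendix C calls them restricted, not prohibited.
- Protocol 5.7 lets the Investigator prescribe to manage AEs. It discontinues subjects who take prohibited medication, or keeps them as major deviations. That this rule covers a new SSRI is an inference from Section 3.1.
- SAP 4 forms the Full Analysis Set from "subjects in the Safety Analysis Set who have both a Baseline value and at least 1 post-Baseline value for the CMAI total score". A subject who starts an SSRI after one post-Baseline CMAI stays in it, even if discontinued.

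So starts should be rare, but the route is open.

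**Inputs for the size.** The plan has no figure to reproduce. From the documents: 111 randomized 1:1:1, so 111/3 = 37 per arm. Everything else is assumed:

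- fraction of baseline users b = 0.3 (range 0.2–0.4)
- fraction p of non-users who start, 1–5%; at b = 0.3 this is 25.9 × 0.01 to 25.9 × 0.05 = 0.26 to 1.30 subjects per arm
- correlation r = 0.3–0.7 between the tendency to start and a poor response
- true drug effect d, in SD units of the change score

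**Model.** Change has SD 1 (higher is worse), with mean 0 on placebo and −d on active. A non-user starts when a normal liability with correlation r to the change exceeds a cut c. With φ the normal density at c:

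- starters sit r·φ/p above their arm mean, and non-starters r·φ/(1−p) below it
- starters make up (1−b)p / [b + (1−b)p] of *Yes*
- error = (active minus placebo within the subgroup) + d

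**A. Starts depend on response only (same cut in both arms), b = 0.3**

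| d | p (placebo) | r | *Yes* | *No* |
|---|---|---|---|---|
| 0.3 | 1% | 0.3 | −0.003 | +0.002 |
| 0.5 | 5% | 0.5 | −0.035 | +0.020 |
| 0.5 | 5% | 0.7 | −0.066 | +0.037 |

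With d = 0 the error in this scenario is 0.

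**B. Start rates differ by arm (placebo 1%, active 5%), any d, b = 0.3**

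| r | *Yes* | *No* |
|---|---|---|
| 0 | 0 | 0 |
| 0.1 | +0.015 | −0.008 |
| 0.3 | +0.046 | −0.024 |
| 0.5 | +0.077 | −0.041 |
| 0.7 | +0.108 | −0.057 |

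Worked line for r = 0.7:

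- Active: φ/p = 2.063 and starters are 0.035/0.335 = 0.104 of *Yes*, so the shift is 0.7 × 2.063 × 0.104 = 0.151.
- Placebo: φ/p = 2.665 and starters are 0.007/0.307 = 0.0228 of *Yes*, so the shift is 0.7 × 2.665 × 0.0228 = 0.043.
- Difference: 0.108.

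Swapping the two rates reverses every sign. At r = 0.7, *Yes* gives 0.169 for b = 0.2 and 0.073 for b = 0.4. A simulation of 4 million per arm at r = 0.5 gave +0.075 and −0.042.

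**Against the noise, before dropout**

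- b = 0.3: SE(*Yes*) = √(2/11.1) = 0.424 and SE(*No*) = √(2/25.9) = 0.278. Largest ratio 0.108/0.424 = 0.26.
- b = 0.2: SE(*Yes*) = √(2/7.4) = 0.520. Largest ratio 0.169/0.520 = 0.32.

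**Cross-check in CMAI points.** Assume an SD of 15–20, starters in the placebo arm only, and starters differing by a fixed amount from baseline users.

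- At 1–2% starting and a 10-point difference, the *Yes* contrast moves 0.15–0.74 points against an SE of 5.5–10.4, or 0.02–0.09 SE.
- At a deliberately extreme corner (10% starting, 15 points, b = 0.2), starters are 0.08/0.28 = 0.286 of *Yes*. The shift is 4.3 points, or 0.41–0.55 SE.

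**The case against.** **Intent and unseen documents.** SAP 8 places the variable among baseline characteristics, so baseline use was probably meant. Two companion documents could already define the flag: SAP 1 states "Specifications for tables, figures, and listings are contained in a separate document", and SAP 5.5 states "The imputation algorithms will be detailed in the analysis dataset specification document". This stands. The text shows a loose rule, not that the analysis will be run wrongly.

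**Starts are rare.** At 1% among about 78 non-users across three arms, the chance that nobody starts is 0.99^78 = 0.46. With no unclear dates the fix would then change nothing. This stands, and it is why the point is minor.

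**Scenario B needs two things at once.** Start rates must differ by arm and starting must also track poor CMAI response; at r = 0 the error is zero. If starts are driven by AEs, a strong correlation with agitation needs its own justification, and the documents supply none. The upper figures are bounds under adverse assumptions, not expectations.

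**The date default often does no harm.** Given the 4-week stability rule, an SSRI with an unclear start date is more likely a baseline drug than a new one, so defaulting to *Yes* would often be right. The weaker case is an unclear stop date that may precede first dose.

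**The analysis is descriptive.** This is one of ten factors in an untested analysis of 111 subjects. That limits the harm, but it does not make a comparison partly defined after randomization a randomized one.

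**Conclusion.** The point holds and is minor. As written, SSRI use is the only one of the ten subgroup factors that can be set by an event on treatment, and the same variable is presented as a baseline characteristic. Under the main assumptions (1–5% of non-users starting, r up to 0.7), the error in a within-subgroup difference ranges from near zero to about a quarter of an SE at 30% baseline users, or a third at 20%. Only the extreme cross-check corner approaches half an SE. The direction cannot be known from the documents. The overall CMAI and ZBI estimates do not use this factor and are unaffected. Use rates, start rates, correlations, effects and SDs are all assumed; only the sample size and the definitions come from the documents.

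**What to change.** In SAP 8 and 12.5, replace the factor with SSRI use at Baseline, Yes or No, where *Yes* means started before first dose and ongoing at first dose. An SSRI known to have stopped before first dose is *No*.

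Exempt this flag from the SAP 5.5 default; relabelling alone would leave that default in force. Resolve unclear start or stop dates only from information recorded up to first dose, under a rule fixed before unblinding. Report SSRIs started on treatment, by arm, in the concomitant-medication table only.

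The cost is one line in each of two SAP sections plus a date rule in the dataset specification. This changes the classification rule as well as the wording. If the companion specifications already define the flag this way, the edit simply brings the SAP into line. The documents do not show whether the database keeps the visit at which each medication was recorded, so the rule must rest on what is actually held. A few subjects with unresolved dates may still be misclassified, but not in a way that depends on treatment.
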